## **3. RESEARCH METHODS**

### **3.1. Study design**

Observational, non-interventional drug and multi-center study in which subjects will be administered as part of routine practice at Korean health care centers by accredited physicians. At least 3000 subjects should be enrolled in this study based on the Article 6 of “Basic Standards for the Re-examination of New Medicines” notified by MFDS. However, with additional 3 years of study period, at least 100 subjects who are being treated with Inlyta within the approved indication will be studied for total of 9 years according to the review result by the MFDS per Pfizer’s request to adjust the number of subjects. The study can be performed in Korean health care centers where INLYTA® is prescribed for advanced renal cell carcinoma (aRCC) after failure of one prior systemic therapy which is the indication for INLYTA® and where post-marketing study is allowed by institutions.

To achieve the target sample size, the study is being conducted in prospective study design and retrospective study design.

Patients to whom INLYTA® is first administered or patients who are already on INLYTA® during the study period should be enrolled in the study. Observation should be done from treatment initiation of INLYTA® for at least 28 calendar days. There are no visits or activities mandated by this study and routine observation will be done during INLYTA® treatment.

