**3.5.4.8. Administrative Status for Study Drug**

INLYTA® is provided by the physician's prescription and Pfizer Korea will not provide drug for this study.

Record the following with regard to administrative status for the study drug.

- Duration of administration: Record the start date and stop date of the medicated drug (year / month / day). If the medication is being continued at the completion of the study, check the box next to 'ongoing'.
- A single dose: Record the dose (in mg) of study drug. In case of dose titration up or down, record each dose with the periods respectively.
- Daily dosing frequency: Record dosing frequency per day.
- Reason for dose adjustment: Record any remarks if applicable

Refer to LPD for posology and method of administration.

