**Table 2. Best overall response when confirmation of CR and PR required**

Overall response First time point	Overall response Subsequent time point	BEST overall response
CR	CR	CR
CR	PR	SD, PD or PR a
CR	SD	SD provided minimum criteria for SD duration met, otherwise, PD
CR	PD	SD provided minimum criteria for SD duration met, otherwise, PD
CR	NE	SD provided minimum criteria for SD duration met, otherwise NE
PR	CR	PR
PR	PR	PR

PR	SD	SD
PR	PD	SD provided minimum criteria for SD duration met, otherwise, PD
PR	NE	SD provided minimum criteria for SD duration met, otherwise NE
NE	NE	NE
CR = complete response, PR = partial response, SD = stable disease, PD = progressive disease, and NE = inevaluable.		
a If a CR is truly met at first time point, then any disease seen at a subsequent time point, even disease meeting PR criteria relative to baseline, makes the disease PD at that point (since disease must have reappeared after CR). Best response would depend on whether minimum duration for SD was met. However, sometimes 'CR' may be claimed when subsequent scans suggest small lesions were likely still present and in fact the patient had PR, not CR at the first time point. Under these circumstances, the original CR should be changed to PR and the best response is PR.		

Patients with a global deterioration of health status requiring discontinuation of treatment without objective evidence of disease progression at that time should be reported as 'symptomatic deterioration'. Every effort should be made to document objective progression even after discontinuation of treatment. Symptomatic deterioration is not a descriptor of an objective response: it is a reason for stopping study therapy. The objective response status of such patients is to be determined by evaluation of target and non-target lesions.

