4.2. Efficacy Endpoints

- Tumor response based on RECIST 1.1
- Objective Response Rate (ORR)

ORR will be defined as the number of subjects who achieve a best overall response of complete response (CR) or partial response (PR), divided by the total number of subjects in efficacy analysis set.

- Progression-free survival (PFS)

PFS is defined as the time from first dose of study medication to first documentation of objective tumor progression, or to death due to any cause, whichever occurs first.

- Time to progression (TTP)

TTP is defined as the time from the first dose of study medication to objective tumor progression excluding death.

5. General Consideration

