6.3. Efficacy Analyses

Efficacy analyses will be performed based on data of efficacy analysis set.

- 1) Best overall response [Complete response (CR), Partial response (PR), Stable disease (SD), Progressive disease (PD), Not evaluable (NE)] will be presented in frequency and percentage.
- 2) Objective response rate (ORR) will be presented in frequency and percentage.

Objective response rate (ORR)

$$= \frac{\text{Number of subjects who achieves a best overall response of CR or PR}}{\text{Number of subjects in the efficacy analysis set}}$$

Statistical Analysis Plan for rPMS

- 3) Kaplan-Meier curve for time-to-event endpoints will be generated and presented quartiles with 95% CI, event rates and censor rates. Date of death is date of resolution of serious adverse event in which the category of seriousness is 'Results in death'. In case subjects do not have an event, censor of time-to-event is performed at the date of final follow-up.
 - Progression-free survival (PFS)
 - Time to progression (TTP)
- 4) Objective response rate (ORR) by demographic and other baseline characteristics
 - Objective response rate and 95% CI will be presented by categorical variables of demographic and other baseline characteristics.
 - To identify statistically significant difference in objective response rate by categorical variables of demographic and other baseline characteristics, Chi-square test (χ^2 test) or Fisher's exact test (if the expected frequency for each cell under 5 is more than 20%) will be performed.
- 5) Analysis of factors that affect the efficacy
 - In the re-examination report, logistic regression or multivariate analysis will be performed and an odds ratio with 95% CI and p-value will be presented to identify the factors that affect objective response rate in demographic and other baseline characteristics.

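### Patients who stop INLYTA for deterioration without documented progression are plain Kaplan-Meier censoring, so PFS is probably overstated for those stops; deaths are censored in TTP, so its curve is not progression incidence

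*SAP*

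**What the plan says.** **Endpoints (SAP 4.2).** PFS runs from first dose to "first documentation of objective tumor progression, or to death due to any cause, whichever occurs first". For the other endpoint, "TTP is defined as the time from the first dose of study medication to objective tumor progression excluding death".

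**Analysis (SAP 6.3, item 3).** "Kaplan-Meier curve for time-to-event endpoints will be generated and presented quartiles with 95% CI, event rates and censor rates". The only censoring rule is "In case subjects do not have an event, censor of time-to-event is performed at the date of final follow-up". Neither document defines the date of final follow-up, although SAP 5.2.2 also uses it to fill in an ongoing end date for study drug. On deaths: "Date of death is date of resolution of serious adverse event in which the category of seriousness is 'Results in death". No sensitivity analysis is named; SAP 5.2.1 says only that the effect of missing data will be assessed where appropriate.

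**Follow-up.** Protocol 3.1: "There are no visits or activities mandated by this study and routine observation will be done during INLYTA® treatment". Protocol Appendix 4, under best overall response: "Every effort should be made to document objective progression even after discontinuation of treatment". The same paragraph says that patients who deteriorate and must stop without objective progression should be reported as symptomatic deterioration, and that this is a reason for stopping rather than a response category.

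**Data fields.** Protocol 3.5.4.8 asks for start and stop dates, dose and frequency, and "Reason for dose adjustment: Record any remarks if applicable"; it lists no reason for permanent stop. Protocol 3.5.4.10 asks for the scan date and the overall response. The SAP does not use the symptomatic deterioration category.

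**Safety route.** Under Protocol 3.5.4.9.1 and 5.2.2, progression is not reported as an SAE unless it is fatal. Under Protocol 5.1.2 the reporting period must reach at least 28 days after the last dose. After study completion, an SAE has to be reported only if the investigator considers it related to INLYTA.

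**The concern.** Kaplan-Meier is valid when patients censored at a given time have the same later risk as those still followed. A patient taken off INLYTA because of clinical decline does not obviously meet that condition. With no scans mandated and routine observation tied to treatment, progression in such a patient may never be recorded as an objective event. If death follows outside the required reporting window, it may not become a PFS event either. These patients then count as censored although many have in truth failed, and the PFS quartiles move upward. Tables 27 and 28 show a censored rate without reasons, so a reader of the final report could not judge how much this matters.

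TTP raises a different question. Death is censored there by definition. A reader who takes one minus the TTP curve as the share of patients seen to progress will misread it.

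PFS and TTP are two of the four efficacy endpoints in Protocol 3.5.3.2, and they go into a regulatory re-examination report.

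**Working it through.** The plan states no median, hazard, event count or expected share of stops, so there is no figure to reproduce. The estimator, the event definitions and the censoring rule come from SAP 4.2 and 6.3. The shares, hazard ratios and the 7-month median below are assumptions, shown as ranges. All hazards are constant.

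**A. PFS, final follow-up close to the stop.** Measure time in units of the reported KM median, so the hazard on follow-up is λ = ln 2 = 0.693. A share s leaves before a documented event, at rate μ = λs/(1−s), and then has hazard kλ. True survival is

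S(t) = exp(−(λ+μ)t) + [μ/(λ+μ−kλ)]·[exp(−kλt) − exp(−(λ+μ)t)].

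Example with s = 20%, k = 2: μ = 0.173, λ+μ = 0.866, kλ = 1.386. At t = 0.940, S = 0.443 + (−0.333)(0.272 − 0.443) = 0.500. The true median is 0.940, and KM overstates it by 1/0.940 − 1 = 6%.

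True median, with the error of the KM median in brackets:

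| s | k = 0.5 | k = 1 | k = 2 | k = 4 | fails at exit |
|---|---|---|---|---|---|
| 10% | 1.022 (−2%) | 1.000 (0%) | 0.971 (+3%) | 0.942 (+6%) | 0.900 (+11%) |
| 20% | 1.050 (−5%) | 1.000 (0%) | 0.940 (+6%) | 0.882 (+13%) | 0.800 (+25%) |
| 30% | 1.088 (−8%) | 1.000 (0%) | 0.906 (+10%) | 0.822 (+22%) | 0.700 (+43%) |

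The last column is 1/(1−s) − 1, the ceiling. A simulation with 100 patients and s = 20% agrees: mean KM median against true median was 1.01 v 0.93 (k = 2), 1.01 v 0.88 (k = 4) and 1.01 v 1.04 (k = 0.5).

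**B. PFS, final follow-up long after the stop, with no scans in between.** Stoppers stay in the risk set as event-free. The KM curve tends to 1 − (1−s)(1 − exp(−(λ+μ)t)), whose median is 1.053, 1.132 and 1.265 for s = 10%, 20% and 30%. Against a true median of 1.000 at k = 1, that is +5%, +13% and +27%, even with no excess hazard after stopping.

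**C. TTP.** Assume a PFS median of 7 months, so λ = ln 2/7 = 0.0990 per month, and let a share q of first events be deaths. At 12 months:

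- 1−KM = 1 − exp(−(1−q)·12λ)
- cumulative incidence of progression = (1−q)(1 − exp(−12λ))

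| q | 1−KM | cumulative incidence | gap (points) |
|---|---|---|---|
| 10% | 65.7% | 62.6% | 3.1 |
| 20% | 61.3% | 55.6% | 5.7 |
| 30% | 56.5% | 48.7% | 7.8 |

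On the time scale with q = 20%, the KM median is 7/0.8 = 8.75 months, while cumulative incidence reaches 50% at −ln(1 − 0.5/0.8)/λ = 9.9 months. Read as incidence, the KM curve shows more progression, and earlier, than would be observed.

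**The case against.** **The rule censors at final follow-up, not at stopping.** Progression or death recorded between the two still counts. A fatal malignancy during the study or within the safety reporting period must be recorded as a Grade 5 SAE, which makes it a PFS event. This stands and narrows the point to non-fatal deterioration and to deaths that no SAE report captures. It does not remove it: whether final follow-up falls early (check A, with k above 1) or late (check B), the error for deterioration stops is upward.

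**Protocol 3.1 does not forbid later data.** It sets a minimum observation period, and Appendix 4 asks only for effort. This stands in part. The texts are in tension rather than flatly contradictory, but a site following Protocol 3.1 alone could reasonably end efficacy collection when INLYTA stops.

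**Related data are collected elsewhere.** Protocol 3.5.4.9.1 records the action taken for each adverse event, including permanent discontinuation. Protocol 5.1.1 puts lack of efficacy on the CRF. Protocol 4.3 asks why a patient withdraws from the study. That is correct, so the gap is narrow: no listed field identifies symptomatic deterioration as the reason for stopping, and SAP 6.2 pools permanent, temporary and delayed discontinuation.

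**Excluding death is the stated TTP definition.** This stands. With independent constant hazards, as in check C, KM is a valid estimate of that quantity. Cumulative incidence answers a different question, and the issue is interpretation.

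**The consequence is limited.** The objective is monitoring of use and adverse events. Efficacy is descriptive and single-arm, with no PFS or TTP hypothesis, and Protocol 3.5.3.2 already describes PFS as subject to limited follow-up. This stands. Type I error and power are untouched. However, SAP 4.2 drops the qualifier, and the plan offers nothing to gauge its effect.

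**Conclusion.** The point holds for PFS in patients who stop for deterioration: the plan can lose true failures, and median PFS is probably overstated. The 3–22% range rests on assumed shares of 10–30% and later hazards 2–4 times higher. The 11–43% figures are a ceiling that applies only if every such exit is itself a failure, so they should not be quoted as the expected bias.

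A reader might go further and infer three things that the documents do not support:

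- **That all stops without progression inflate PFS.** For toxicity stops nothing in the documents gives the later hazard. At k = 1 there is no error under check A, and at k = 0.5 PFS is understated by 2–8%.
- **That TTP is too optimistic because deaths are censored.** Check C shows the reverse when the curve is read as incidence. Optimism from deaths would need positively related risks of death and progression, on which the documents are silent.
- **That censoring deaths in TTP is an error.** It follows from the definition. What is missing is an output that gives the probability of observed progression.

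This is a cheap and worthwhile improvement to two descriptive efficacy endpoints. It does not threaten the study's safety objective.

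**What to change.** 1. **Reconcile Protocol 3.1 with Appendix 4, and define final follow-up.** State in Protocol 3.1 and 3.5.4.10 that routine scan results and vital status already in the chart are collected after INLYTA stops, until progression, death, new anticancer therapy or study end. No scan or visit is added. In SAP 6.3(3), define the date of final follow-up and let a death found through chart vital status count as a PFS event.
2. **Record the reason for permanent stop.** Add one field under Protocol 3.5.4.8, with symptomatic deterioration as an option. Add a PFS sensitivity analysis that counts a stop for symptomatic deterioration as an event on the stop date, reported beside Table 27.
3. **Report cumulative incidence for TTP.** In SAP 6.3(3) and Table 28, show the cumulative incidence of progression, with death as a competing event, beside the Kaplan-Meier curve.

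**Cost.** A protocol and SAP amendment, one CRF field, two extra outputs, and chart abstraction for about 100 patients. Collection began in December 2012, so earlier charts would have to be reopened. That must stay within the consent given, and Protocol 4.3 bars further collection from anyone who has withdrawn consent for disclosure. Reported PFS may become shorter.

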6.4. Sub-Group Analyses

The following analyses will be performed for subjects who are prescribed with INLYTA® for the first time and for subjects who are already on INLYTA®, separately.

- 1) [6.2. Safety Analyses] - 1) ~ 4)
- 2) [6.3. Efficacy Analyses] - 1) ~ 5)

7. Reporting Conventions

Continuous variables will be summarized by descriptive statistics including n, mean, SD, SE, median, minimum and maximum, and categorical variables will be presented in frequency and percentage. Summary statistics including mean, SD, SE, median, minimum and maximum, etc. will be reported to two decimal places using rounding off.

The p-values through the statistical test will be reported to four decimal place and if p-values smaller than 0.0001 will be written as '<0.0001'.

8. Attachments

[Table 22] Adverse events by action	18
[Table 23] Occurrence status of adverse events by demographic characteristics	19
[Table 24] Occurrence status of adverse events by other baseline characteristics.....	19
[Table 25] Multivariate logistic regression for occurrence status of adverse events	21
[Table 26] Best overall response and objective response rate	21
[Table 27] Summary statistics for progression-free survival	22
[Table 28] Summary statistics for time to progression.....	23
[Table 29] Objective response rate by demographic characteristics	24
[Table 30] Objective response rate by demographic and other baseline characteristics	24
[Table 31] Multivariate logistic regression for objective response rate	26
[Table 32] Adverse events and adverse drug reactions of pediatric subjects (aged < 19) (N=xxx)	27
[Table 33] Adverse events and adverse drug reactions of geriatric subjects (aged ≥ 65) (N=xxx)	27
[Table 34] Adverse events and adverse drug reactions in the subjects with renal impairment (N=xxx)	27

Dummy Table

[Table 35] Adverse events and adverse drug reactions in the subjects with hepatic impairment (N=xxx)	27
[Table 36] Reasons for excluding safety evaluation (N=xxx).....	28
[Table 37] Adverse events and adverse drug reactions in the subjects excluded from safety analysis (N=xxx).....	28

LIST OF FIGURE

[Figure 1] Kaplan-Meier curve for progression-free survival	22
[Figure 2] Kaplan-Meier curve for time to progression	23

Dummy Table

[Table 1] Demographic characteristics

Factor	Classification	Number of subjects n(%)
Sex	Male	xxx(xx.xx)
	Female	xxx(xx.xx)
	Total	xxx(xx.xx)
Age (year)	n	xxx
	Mean±SD	xx.xx±xx.xx
	Median	xx.xx
	Min~Max	xx.xx~xx.xx
	Category 1	xxx(xx.xx)
	Category 2	xxx(xx.xx)
	Category 3	xxx(xx.xx)
	...	xxx(xx.xx)
	Total	xxx(xx.xx)
Pediatric	< 19 years	xxx(xx.xx)
	≥ 19 years	xxx(xx.xx)
	Total	xxx(xx.xx)
Geriatric	≥ 65 years	xxx(xx.xx)
	< 65 years	xxx(xx.xx)
	Total	xxx(xx.xx)
Classification	Outpatient	xxx(xx.xx)
	Inpatient	xxx(xx.xx)
	Total	xxx(xx.xx)
Height (cm)	n	xxx
	Mean±SD	xx.xx±xx.xx
	Median	xx.xx
	Min~Max	xx.xx~xx.xx
Weight (kg)	n	xxx
	Mean±SD	xx.xx±xx.xx
	Median	xx.xx
	Min~Max	xx.xx~xx.xx

[†]Number of missing

Programming note: The categories of age will be set considering distribution of data.

[Table 2] Other baseline characteristics

Factor	Classification	Number of subjects n(%)
Duration of aRCC (month)	n	xxx
	Mean±SD	xx.xx±xx.xx
	Median	xx.xx
	Min~Max	xx.xx~xx.xx
	Category 1	xxx(xx.xx)
	Category 2	xxx(xx.xx)
	Category 3	xxx(xx.xx)
	...	xxx(xx.xx)
	Total	xxx(xx.xx)
Cell component of aRCC	Clear cell	xxx(xx.xx)
	Other	xxx(xx.xx)
	Total	xxx(xx.xx)
Metastasis	Yes [§]	xxx(xx.xx)

Dummy Table

Factor	Classification	Number of subjects n(%)
	Liver	xxx(xx.xx)
	Lung	xxx(xx.xx)
	Bone	xxx(xx.xx)
	Brain	xxx(xx.xx)
	Skin	xxx(xx.xx)
	Lymph nodes	xxx(xx.xx)
	Other	xxx(xx.xx)
	No	xxx(xx.xx)
	Total	xxx(xx.xx)
Primary lesion surgery	Done	xxx(xx.xx)
	Not done	xxx(xx.xx)
	Total	xxx(xx.xx)
Medical history	Yes	xxx(xx.xx)
	No	xxx(xx.xx)
	Total	xxx(xx.xx)
Renal impairment	Yes	xxx(xx.xx)
	No	xxx(xx.xx)
	Total	xxx(xx.xx)
Hepatic impairment	Yes	xxx(xx.xx)
	No	xxx(xx.xx)
	Total	xxx(xx.xx)
Allergic history	Yes	xxx(xx.xx)
	No	xxx(xx.xx)
	Total	xxx(xx.xx)
Prior chemotherapy	Yes	xxx(xx.xx)
	No	xxx(xx.xx)
	Unknown	xxx(xx.xx)
	Total	xxx(xx.xx)
Prior immunotherapy	Yes	xxx(xx.xx)
	No	xxx(xx.xx)
	Unknown	xxx(xx.xx)
	Total	xxx(xx.xx)
Prior radiation therapy	Yes	xxx(xx.xx)
	No	xxx(xx.xx)
	Unknown	xxx(xx.xx)
	Total	xxx(xx.xx)
Concomitant medication	Yes	xxx(xx.xx)
	No	xxx(xx.xx)
	Total	xxx(xx.xx)

[†]Number of missing

[§]Overlapped

Dummy Table

[Table 3] Medical history

Medical history	n(%), [E]
Yes	xxx(xx.xx), [xxx]
No	xxx(xx.xx)
Total	xxx(xx.xx)
System Organ Class[§]	n(%), [E]
Preferred Term	
System Organ Class	xxx(xx.xx), [xxx]
Preferred Term	xxx(xx.xx), [xxx]
...	xxx(xx.xx), [xxx]

[§]Overlapped, MedDRA latest version

E: Number of events

¹⁾Renal impairment (xxx subjects (xx.xx%), xxx events)

²⁾Hepatic impairment (xxx subjects (xx.xx%), xxx events)

[Table 4] Prior chemotherapy

Prior chemotherapy	n(%), [E]
Yes	xxx(xx.xx), [xxx]
No	xxx(xx.xx)
Unknown	xxx(xx.xx)
Total	xxx(xx.xx)
Level 1[§]	n(%), [E]
Level 2	
Level 1	xxx(xx.xx), [xxx]
Level 2	xxx(xx.xx), [xxx]
...	xxx(xx.xx), [xxx]

[§]Overlapped, ATC Classification System latest version

E: Number of events

[Table 5] Prior immunotherapy

Prior immunotherapy	n(%), [E]
Yes	xxx(xx.xx), [xxx]
No	xxx(xx.xx)
Unknown	xxx(xx.xx)
Total	xxx(xx.xx)
Level 1[§]	n(%), [E]
Level 2	
Level 1	xxx(xx.xx), [xxx]
Level 2	xxx(xx.xx), [xxx]
...	xxx(xx.xx), [xxx]

[§]Overlapped, ATC Classification System latest version

E: Number of events

Dummy Table

[Table 6] Concomitant medication

Concomitant medication	n(%), [E]
Yes	xxx(xx.xx), [xxx]
No	xxx(xx.xx)
Total	xxx(xx.xx)
Level 1[§]	
Level 2	n(%), [E]
Level 1	xxx(xx.xx), [xxx]
Level 2	xxx(xx.xx), [xxx]
...	xxx(xx.xx), [xxx]

[§]Overlapped, ATC Classification System latest version

E: Number of events

[Table 7] Administrative status for INLYTA®

Factor	Classification	Number of subjects n(%)
Period of first administration [†]	Sub-group 1	xxx(xx.xx)
	Sub-group 2	xxx(xx.xx)
	Total	xxx(xx.xx)
Duration of administration (day)	n	xxx
	Mean±SD	xx.xx±xx.xx
	Median	xx.xx
	Min~Max	xx.xx~xx.xx
	Category 1	xxx(xx.xx)
	Category 2	xxx(xx.xx)
	Category 3	xxx(xx.xx)
	...	xxx(xx.xx)
	Total	xxx(xx.xx)
Total dose (mg)	n	xxx
	Mean±SD	xx.xx±xx.xx
	Median	xx.xx
	Min~Max	xx.xx~xx.xx
Daily average dose (mg/day)	n	xxx
	Mean±SD	xx.xx±xx.xx
	Median	xx.xx
	Min~Max	xx.xx~xx.xx
	Category 1	xxx(xx.xx)
	Category 2	xxx(xx.xx)
	Category 3	xxx(xx.xx)
	...	xxx(xx.xx)
	Total	xxx(xx.xx)

[†]Sub-group 1: Subjects who are first administered INLYTA® during the study period

Sub-group 2: Subjects who has continued administration of INLYTA® since the time prior to the contract date

Dummy Table

[Table 8] Summary of incidence of adverse events

Adverse Events	Sub-group 1 (N=xxx) n(%), [E]	Sub-group 2 (N=xxx) n(%), [E]	Total (N=xxx) n(%), [E]
Serious adverse events	xxx(xx.xx), [xxx]	xxx(xx.xx), [xxx]	xxx(xx.xx), [xxx]
Serious adverse drug reactions	xxx(xx.xx), [xxx]	xxx(xx.xx), [xxx]	xxx(xx.xx), [xxx]
Unexpected serious adverse events	xxx(xx.xx), [xxx]	xxx(xx.xx), [xxx]	xxx(xx.xx), [xxx]
Unexpected serious adverse drug reactions	xxx(xx.xx), [xxx]	xxx(xx.xx), [xxx]	xxx(xx.xx), [xxx]
Unexpected adverse events	xxx(xx.xx), [xxx]	xxx(xx.xx), [xxx]	xxx(xx.xx), [xxx]
Unexpected adverse drug reactions	xxx(xx.xx), [xxx]	xxx(xx.xx), [xxx]	xxx(xx.xx), [xxx]
Adverse events	xxx(xx.xx), [xxx]	xxx(xx.xx), [xxx]	xxx(xx.xx), [xxx]
Adverse drug reactions	xxx(xx.xx), [xxx]	xxx(xx.xx), [xxx]	xxx(xx.xx), [xxx]

Sub-group 1: Subjects who are first administered INLYTA® during the study period

Sub-group 2: Subjects who has continued administration of INLYTA® since the time prior to the contract date

E: number of adverse events

Dummy Table

[Table 9] Serious adverse events and serious adverse drug reactions

System Organ Class [§] Preferred Term	Serious adverse events		Serious adverse drug reactions	
	n(%), [E]	[95% CI]	n(%), [E]	[95% CI]
System Organ Class Preferred Term	xxx(xx.xx), [xxx] xxx(xx.xx), [xxx] xxx(xx.xx), [xxx] xxx(xx.xx), [xxx]	[xx.xx, xx.xx] [xx.xx, xx.xx] [xx.xx, xx.xx]	xxx(xx.xx), [xxx] xxx(xx.xx), [xxx] xxx(xx.xx), [xxx]	[xx.xx, xx.xx] [xx.xx, xx.xx] [xx.xx, xx.xx]
Total	xxx(xx.xx), [xxx]	[xx.xx, xx.xx]	xxx(xx.xx), [xxx]	[xx.xx, xx.xx]

[§]Overlapped, MedDRA latest version
E: Number of adverse events

Programming note: This table is repeated for each sub-group with the following table title and footnote.

*Title : [Table 9-*x*] Serious adverse events and serious adverse drug reactions (sub-group *x*: N=xxx)*

Footnote: Sub-group 1: Subjects who are first administered INLYTA® during the study period

Sub-group 2: Subjects who has continued administration of INLYTA® since the time prior to the contract date

[Table 10] Details of serious adverse events

Subject No.	Sub-group [†]	System Organ Class [§]	Preferred Term [§]	Date of onset	Severity	Outcome	Seriousness	adverse event to INLYTA®	Other causality of adverse event	Action	Expected ness
Sxxx-xxx	Sub-group x	System Organ Class	Preferred Term	YYYY-MM-DD	xxx	xxx	xxx	xxx	xxx	xxx	xxx
Sxxx-xxx	Sub-group x	System Organ Class	Preferred Term	YYYY-MM-DD	xxx	xxx	xxx	xxx	xxx	xxx	xxx

[†]Sub-group 1: Subjects who are first administered INLYTA® during the study period

Sub-group 2: Subjects who has continued administration of INLYTA® since the time prior to the contract date

[§]MedDRA latest version

Programming note: This analysis will be performed in the re-examination report only.

Dummy Table

[Table 11] Unexpected serious adverse events and unexpected serious adverse drug reactions

System Organ Class [§] Preferred Term	Unexpected serious adverse events		Unexpected serious adverse drug reactions	
	n(%), [E]	[95% CI]	n(%), [E]	[95% CI]
System Organ Class Preferred Term	xxx(xx.xx), [xxx]	[xx.xx, xx.xx]	xxx(xx.xx), [xxx]	[xx.xx, xx.xx]
	xxx(xx.xx), [xxx]	[xx.xx, xx.xx]	xxx(xx.xx), [xxx]	[xx.xx, xx.xx]
	xxx(xx.xx), [xxx]	[xx.xx, xx.xx]	xxx(xx.xx), [xxx]	[xx.xx, xx.xx]
Total	xxx(xx.xx), [xxx]	[xx.xx, xx.xx]	xxx(xx.xx), [xxx]	[xx.xx, xx.xx]

[§]Overlapped, MedDRA latest version

E: Number of adverse events

Programming note: This table is repeated for each sub-group with the following table title and footnote.

Title : [Table 11-x] Unexpected serious adverse events and unexpected serious adverse drug reactions (sub-group x: N=xxx)

Footnote: Sub-group 1: Subjects who are first administered INLYTA® during the study period

Sub-group 2: Subjects who has continued administration of INLYTA® since the time prior to the contract date

[Table 12] Details of unexpected serious adverse events

Subject No.	Sub-group [†]	System Organ Class [§]	Preferred Term [§]	Date of onset	Severity	Outcome	Seriousness	Causality of adverse event to INLYTA®	Other causality of adverse event	Action
Sxxxxxx	Sub-group x	System Organ Class	Preferred Term	YYYY-MM-DD	xxx	xxx	xxx	xxx	xxx	xxx
Sxxxxxx	Sub-group x	System Organ Class	Preferred Term	YYYY-MM-DD	xxx	xxx	xxx	xxx	xxx	xxx

[†]Sub-group 1: Subjects who are first administered INLYTA® during the study period

Sub-group 2: Subjects who has continued administration of INLYTA® since the time prior to the contract date

[§]MedDRA latest version

Programming note: This analysis will be performed in the re-examination report only.

Dummy Table

[Table 13] Unexpected adverse events and unexpected adverse drug reactions

System Organ Class [§] Preferred Term	Unexpected adverse events		Unexpected adverse drug reactions	
	n(%), [E]	[95% CI]	n(%), [E]	[95% CI]
System Organ Class Preferred Term	xxx(xx.xx), [xxx]	[xx.xx, xx.xx]	xxx(xx.xx), [xxx]	[xx.xx, xx.xx]
	xxx(xx.xx), [xxx]	[xx.xx, xx.xx]	xxx(xx.xx), [xxx]	[xx.xx, xx.xx]
	xxx(xx.xx), [xxx]	[xx.xx, xx.xx]	xxx(xx.xx), [xxx]	[xx.xx, xx.xx]
Total	xxx(xx.xx), [xxx]	[xx.xx, xx.xx]	xxx(xx.xx), [xxx]	[xx.xx, xx.xx]

[§]Overlapped, MedDRA latest version
E: Number of adverse events

Programming note: This table is repeated for each sub-group with the following table title and footnote.

Title : [Table 13-x] Unexpected adverse events and unexpected adverse drug reactions (sub-group x: N=xxx)

Footnote: Sub-group 1: Subjects who are first administered INLYTA® during the study period

Sub-group 2: Subjects who has continued administration of INLYTA® since the time prior to the contract date

[Table 14] Details of unexpected adverse events

Subject No.	Sub-group [†]	System Organ Class [§]	Preferred Term [§]	Date of onset	Date of resolution	Severity	Outcome	Seriousness	Causality of adverse event to INLYTA®	Other causality of adverse event	Action
Sxxx-xxx	Sub-group x	System Organ Class	Preferred Term	YYYY-MM-DD	YYYY-MM-DD	xxx	xxx	xxx	xxx	xxx	xxx
Sxxx-xxx	Sub-group x	System Organ Class	Preferred Term	YYYY-MM-DD	YYYY-MM-DD	xxx	xxx	xxx	xxx	xxx	xxx

[†]Sub-group 1: Subjects who are first administered INLYTA® during the study period

Sub-group 2: Subjects who has continued administration of INLYTA® since the time prior to the contract date

[§]MedDRA latest version

Programming note: This analysis will be performed in the re-examination report only.

Dummy Table

[Table 15] Adverse events and adverse drug reactions

System Organ Class [§] Preferred Term	Adverse events			Adverse drug reactions	
	n(%, [E])	[95% CI]	n(%, [E])	[95% CI]	
System Organ Class Preferred Term	xxx(xx.xx), [xxx]	[xx.xx, xx.xx]	xxx(xx.xx), [xxx]	[xx.xx, xx.xx]	
...	xxx(xx.xx), [xxx]	[xx.xx, xx.xx]	xxx(xx.xx), [xxx]	[xx.xx, xx.xx]	
Total	xxx(xx.xx), [xxx]	[xx.xx, xx.xx]	xxx(xx.xx), [xxx]	[xx.xx, xx.xx]	

[§]Overlapped, MedDRA latest version
E: Number of adverse events

Programming note: This table is repeated for each sub-group with the following table title and footnote.

Title : [Table 15-x] Adverse events and adverse drug reactions (sub-group x: N=xxx)

Footnote: Sub-group 1: Subjects who are first administered INLYTA® during the study period

Sub-group 2: Subjects who has continued administration of INLYTA® since the time prior to the contract date

[Table 16] Adverse events by their severity

System Organ Class [§] Preferred Term	Number of adverse events by their severity [†] (%)				
	Grade 1	Grade 2	Grade 3	Grade 4	Grade 5
System Organ Class Preferred Term	xxx(xx.xx)	xxx(xx.xx)	xxx(xx.xx)	xxx(xx.xx)	xxx(xx.xx)
...	xxx(xx.xx)	xxx(xx.xx)	xxx(xx.xx)	xxx(xx.xx)	xxx(xx.xx)
Total	xxx(xx.xx)	xxx(xx.xx)	xxx(xx.xx)	xxx(xx.xx)	xxx(xx.xx)

[§]MedDRA latest version

[†]Severity evaluation of adverse event must be done according to the NCI CTC grade

Programming note: This table is repeated for each sub-group with the following table title and footnote.

Title : [Table 16-x] Adverse events by their severity (sub-group x: N=xxx)

Footnote: Sub-group 1: Subjects who are first administered INLYTA® during the study period

Sub-group 2: Subjects who has continued administration of INLYTA® since the time prior to the contract date

Dummy Table

[Table 17] Adverse events by their outcome

System Organ Class [§] Preferred Term	Number of adverse events by their outcome (%)			
	Recovered	Recovered with sequelae	Recovering	Not recovered
System Organ Class				
Preferred Term	xxx(xx.xx)	xxx(xx.xx)	xxx(xx.xx)	xxx(xx.xx)
...	xxx(xx.xx)	xxx(xx.xx)	xxx(xx.xx)	xxx(xx.xx)
Total	xxx(xx.xx)	xxx(xx.xx)	xxx(xx.xx)	xxx(xx.xx)

§MedDRA latest version

Programming note: This table is repeated for each sub-group with the following table title and footnote.

Title : [Table 17-x] Adverse events by their outcome (sub-group x: N=xxx)

Footnote: Sub-group 1: Subjects who are first administered INLYTA® during the study period

Sub-group 2: Subjects who has continued administration of INLYTA® since the time prior to the contract date

Dummy Table

[Table 18] Adverse events by their seriousness

		Number of adverse events by their seriousness (%)						
System Organ Class [§] Preferred Term	Results in death Is life-threatening	Requires inpatient hospitalization or prolongation of hospitalization	Results in persistent or significant disability /incapacity	Results in congenital anomaly /birth defect	Other important medical event	Non-SAE	Total	
System Organ Class Preferred Term								
	xxx(xx.xx)	xxx(xx.xx)	xxx(xx.xx)	xxx(xx.xx)	xxx(xx.xx)	xxx(xx.xx)	xxx(xx.xx)	xxx(xx.xx)
	xxx(xx.xx)	xxx(xx.xx)	xxx(xx.xx)	xxx(xx.xx)	xxx(xx.xx)	xxx(xx.xx)	xxx(xx.xx)	xxx(xx.xx)
	xxx(xx.xx)	xxx(xx.xx)	xxx(xx.xx)	xxx(xx.xx)	xxx(xx.xx)	xxx(xx.xx)	xxx(xx.xx)	xxx(xx.xx)
Total	xxx(xx.xx)	xxx(xx.xx)	xxx(xx.xx)	xxx(xx.xx)	xxx(xx.xx)	xxx(xx.xx)	xxx(xx.xx)	xxx(xx.xx)

[§]Overlapped, MedDRA latest version

Programming note: This table is repeated for each sub-group with the following table title and footnote.

Title : [Table 18-x] Adverse events by their seriousness (sub-group x: N=xxx)

Footnote: Sub-group 1: Subjects who are first administered INLYTA® during the study period

Sub-group 2: Subjects who has continued administration of INLYTA® since the time prior to the contract date

Dummy Table

[Table 19] Relation of adverse event to INLYTA®

Relation of adverse event to INLYTA®	Number of adverse events (%)
Related to INLYTA®	xxx(xx.xx)
Not related to INLYTA®	xxx(xx.xx)
Total	xxx(xx.xx)

Programming note: This table is repeated for each sub-group with the following table title and footnote.

Title : [Table 19-x] Relation of adverse event to INLYTA® (sub-group x: N=xxx)

Footnote: Sub-group 1: Subjects who are first administered INLYTA® during the study period

Sub-group 2: Subjects who has continued administration of INLYTA® since the time prior to the contract date

[Table 20] Adverse events by their causality to INLYTA®

System Organ Class [§] Preferred Term	Number of adverse events by their causality to INLYTA® (%)				
	Certain	Probable /likely	Possible	Unlikely	Conditional/ Unaccessible/ unclassified unclassifiable applicable
System Organ Class Preferred Term	xxx(xx.xx)	xxx(xx.xx)	xxx(xx.xx)	xxx(xx.xx)	xxx(xx.xx)
	xxx(xx.xx)	xxx(xx.xx)	xxx(xx.xx)	xxx(xx.xx)	xxx(xx.xx)
	xxx(xx.xx)	xxx(xx.xx)	xxx(xx.xx)	xxx(xx.xx)	xxx(xx.xx)
	...				
Total	xxx(xx.xx)	xxx(xx.xx)	xxx(xx.xx)	xxx(xx.xx)	xxx(xx.xx)
§MedDRA latest version					

Programming note: This table is repeated for each sub-group with the following table title and footnote.

Title : [Table 20-x] Adverse events by their causality to INLYTA® (sub-group x: N=xxx)

Footnote: Sub-group 1: Subjects who are first administered INLYTA® during the study period

Sub-group 2: Subjects who has continued administration of INLYTA® since the time prior to the contract date

Dummy Table

[Table 21] Adverse events by their other causality

System Organ Class [§] Preferred Term	Disease under the study	Number of adverse events by their other causality (%)		
		Other disease	Concomitant treatment drug or non-drug	Others
System Organ Class Preferred Term	xxx(xx.xx)	xxx(xx.xx)	xxx(xx.xx)	xxx(xx.xx)
	xxx(xx.xx)	xxx(xx.xx)	xxx(xx.xx)	xxx(xx.xx)
	xxx(xx.xx)	xxx(xx.xx)	xxx(xx.xx)	xxx(xx.xx)
Total	xxx(xx.xx)	xxx(xx.xx)	xxx(xx.xx)	xxx(xx.xx)
§MedDRA latest version				

Programming note: This table is repeated for each sub-group with the following table title and footnote.

Title : [Table 21-x] Adverse events by their other causality (sub-group x: N=xxx)

Footnote: Sub-group 1: Subjects who are first administered INLYTA® during the study period

Sub-group 2: Subjects who has continued administration of INLYTA® since the time prior to the contract date

[Table 22] Adverse events by action

System Organ Class [§] Preferred Term	Discontinuation	Number of adverse events by action (%)		
		Dosage reduced	Dosage increased	No change
System Organ Class Preferred Term	xxx(xx.xx)	xxx(xx.xx)	xxx(xx.xx)	xxx(xx.xx)
	xxx(xx.xx)	xxx(xx.xx)	xxx(xx.xx)	xxx(xx.xx)
	xxx(xx.xx)	xxx(xx.xx)	xxx(xx.xx)	xxx(xx.xx)
Total	xxx(xx.xx)	xxx(xx.xx)	xxx(xx.xx)	xxx(xx.xx)
§MedDRA latest version				

Programming note: This table is repeated for each sub-group with the following table title and footnote.

Title : [Table 22-x] Adverse events by action (sub-group x: N=xxx)

Footnote: Sub-group 1: Subjects who are first administered INLYTA® during the study period

Sub-group 2: Subjects who has continued administration of INLYTA® since the time prior to the contract date

Dummy Table

[Table 23] Occurrence status of adverse events by demographic characteristics

Factor	Classification	No. of Subjects	Incidence of AE n(%)	[95% CI]	p-value ¹⁾²⁾
Sex	Male	xxx	xxx(xx.xx)	[xx.xx, xx.xx]	x.xxxx
	Female	xxx	xxx(xx.xx)	[xx.xx, xx.xx]	
	Total	xxx	xxx(xx.xx)	-	
Age	Category 1	xxx	xxx(xx.xx)	[xx.xx, xx.xx]	x.xxxx
	Category 2	xxx	xxx(xx.xx)	[xx.xx, xx.xx]	
	Category 3	xxx	xxx(xx.xx)	[xx.xx, xx.xx]	
	...	xxx	xxx(xx.xx)	[xx.xx, xx.xx]	
Pediatric	Total	xxx	xxx(xx.xx)	-	
	< 19 years	xxx	xxx(xx.xx)	[xx.xx, xx.xx]	x.xxxx
	≥ 19 years	xxx	xxx(xx.xx)	[xx.xx, xx.xx]	
Geriatric	Total	xxx	xxx(xx.xx)	-	
